The Role of GIP in Postprandial Splanchnic Blood Flow Distribution and Metabolism in Patients with Type 2 Diabetes

Department of Biomedical Sciences,
University of Copenhagen

H-20078806
Date: 10/5/24

Title: The Role of GIP in Postprandial Splanchnic Blood Flow Distribution and Metabolism in Patients with Type 2 Diabetes

Approved ethical committee ID: H-20078806

Project Group:

[name] [name], PhD (PI)
 [name], PhD
 [name], cand.scient.
 [name] [name]
 [name], cand. scient., PhD
 [name], cand. scient., PhD
 [name], cand.scient. PhD
 [name] [name], MD, DMSc
 [name] Bo [name], DMSc
 [name] [name], MD, PhD

Background: In healthy men endogenous glucose-dependent insulinotropic polypeptide (GIP) contribute to the increased abdominal blood flow in the superior mesenteric artery after the ingestion of glucose. Previous studies have established that the GIP receptor is downregulated in patient with type 2 diabetes. With the use of flow sensitive magnetic resonance imaging (MRI), we investigated the effect of endogenous GIP on the gastrointestinal blood flow in patients with type 2 diabetes. Thereby we expect to see a reduced effect of the hormone GIP on the gastrointestinal blood flow.

Aim: The aim of this study is to investigate and describe the changes in blood flow and oxygen tension in the vessels superior mesenteric artery, celiac trunk, arteria hepatica, and vena portae during and after ingestion of glucose or water in patients with type 2 diabetes. Furthermore, we will investigate the effect of endogenous GIP on the postprandial blood flow in patients with type 2 diabetes with an infusion of the GIP receptor antagonist GIP(3-30)NH₂ (1,000 pmol/kg/min).

Hypothesis: The hypothesis of this study is that the intake of glucose will result in a redistribution of blood that increases the blood flow to the intestines and that antagonization of GIP receptor postprandially will have minor to none effect on the redistribution of blood flow in patients with type 2 diabetes – in contrast to what is seen in healthy individuals.

Design:

Randomized, placebo controlled, crossover, single blind design in 10 patients with type 2 diabetes.

Baseline information:

A description of the baseline measured will be presented in a table, including the following measures: Age, Weight, Height, BMI, Hemoglobin, Leucocytes, Vitamin D, Fasting glucose, HbA1c, Sex, and Blood pressure. The data will be presented in Median and range.

Statistical analysis and graphs:

The flow data is analyzed in R studio by a linear mixed model, that pairs the data, and compared the interventions after steady state of the infusion of GIPR antagonist. The primary statistical analysis will be done between the two interventions: GIPR-antagonist infusion + oral glucose ingestion and Saline + oral glucose ingestion. Furthermore, the data will be presented in GraphPad Prism 10. A

data table will present the flow measurements of each intervention, including mean and 95% confidence intervals.

Criteria:

[figure not shown]
Inclusion = Type 2 diabetes (HbA1c > 48 mmol/mol), age 20-80 years, BMI 20-35 kg/m²

Exclusion = GLP-1-based treatment, not MRI-compatible implants, claustrophobia, abnormal kidney or liver function, anemia, planned weight loss or change in diet, hypertension, other conditions that could be expected to affect the primary or secondary outcomes

Interventions:

- 1) Saline infusion + oral water
- 2) Saline infusion + oral glucose tolerance test (OGTT)
- 3) GIP(3-30)NH₂ infusion + oral water
- 4) GIP(3-30)NH₂ infusion + OGTT

Methods and outcomes: Phase-contrast magnetic resonance imaging (PC-MRI) is used to calculate blood flow in the four described vessels during the infusion of either saline or GIP receptor antagonist. The main outcome of the study is *blood flow in superior mesenteric artery*. On each study day, 11 MRI scans are performed (-35 min to 80 min after oral fluid intake) and nine blood samples. Blood glucose is measured bedside on whole blood. The blood samples collected are kept for analysis of GIP(1-42), GIP(3-30)NH₂, glucagon, insulin, and C-peptide.

Adverse event:

All adverse events (AEs) or serious adverse event (SAE) are reported throughout the whole study period, any adverse event reported will be informed to the ethical committee responsible for the study. All AEs including local and systemic reactions not meeting the criteria for SAEs will be captured on the appropriate case report form. Information to be collected includes event description, time of onset, qualified medical professional's assessment of severity, relationship to study product (assessed only by those with the training and authority to make a diagnosis), and time of resolution/stabilization of the event. All AEs occurring while on study must be documented appropriately regardless of relationship. All AEs will be followed to adequate resolution.

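### Single blind is stated without naming the masked party, and no masking is described for whoever calculates PC-MRI flow, so reader expectation could influence the primary contrast

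*Combined protocol and SAP*

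**What the plan says.** The Design section gives the blinding level in one phrase: "Randomized, placebo controlled, crossover, single blind design in 10 patients with type 2 diabetes". It does not say which party is blinded.

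Methods and outcomes names "blood flow in superior mesenteric artery" as the main outcome. It says that PC-MRI "is used to calculate blood flow in the four described vessels during the infusion of either saline or GIP receptor antagonist". It does not say who calculates flow, whether vessel outlines are manual or automated, or whether the files are coded first.

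Statistical analysis and graphs sets the primary comparison as "GIPR-antagonist infusion + oral glucose ingestion and Saline + oral glucose ingestion", which are interventions 4 and 2. It adds: "The flow data is analyzed in R studio by a linear mixed model, that pairs the data". Masking of the analyst, and a data lock before allocation is revealed, are not mentioned.

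The Hypothesis section states in advance that blocking the GIP receptor is expected to change postprandial flow redistribution little or not at all in these patients.

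**The concern.** With a saline placebo infused into patients, single blind ordinarily means that the patient is masked and the staff are not. The primary outcome is derived from images rather than reported by the patient, so masking the patient does little to protect it. The step that needs protection is the calculation of flow, and the plan describes none there.

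The investigators expect no difference. If the person calculating flow knows the infusion, small choices could pull the two glucose days together. The result would then look like support for the hypothesis, in a trial of 10 patients whose plan gives no power calculation and no equivalence margin. A shift in the other direction would produce a false difference.

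Masking is practicable for this contrast. A glucose day may be recognisable from its rise in flow, but both arms of the primary comparison are glucose days, so the rise alone does not reveal the infusion.

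**Working it through.** **Text check.** The documents give a blinding level but no masked party; an outcome calculated from images but no reader, coding or lock; and an expected answer. There is no stated SD, effect size, alpha or power, so there is no figure of the plan's own to reproduce. What follows is illustration.

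**Inputs from the documents.** n = 10 patients, paired comparison of interventions 4 and 2.

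**Assumed inputs.** Two-sided alpha 0.05; a paired t-test on one summary value per glucose day, as a stand-in for the mixed model; a true effect of 15% of mean flow; an SD of the within-patient difference of 10%, 15% or 20% of mean flow; a systematic shift between the two glucose days of 0, 1%, 2% or 5%.

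**Step 1: how far an outline error could move flow.** Suppose outlines are drawn by hand and the drawn radius is x times the true radius.

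- Flat velocity profile: flow follows area, so the fraction lost is 1 − x². At x = 0.98 this is 1 − 0.9604 = 4.0%. At x = 0.97 it is 1 − 0.9409 = 5.9%.
- Parabolic profile: the fraction lost is (1 − x²)². At x = 0.98 this is 0.0396² = 0.16%. At x = 0.97 it is 0.0591² = 0.35%.

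A 2–3% radius error therefore changes flow by about 0.2% to 6%, depending on a profile that the documents do not give. Under a parabolic profile, losing 5% of flow needs (1 − x²)² = 0.05, so x² = 1 − 0.2236 = 0.7764 and x = 0.881: a radius about 12% too small.

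**Step 2: effect on power.** With a shift s towards the null, the noncentrality is √10 × (15 − s)/SD on 9 degrees of freedom, and the critical value is 2.262. For SD 15% and s = 5% it is √10 × 10/15 = 2.11.

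| SD of paired difference | s = 0 | s = 1% | s = 2% | s = 5% |
|---|---|---|---|---|
| 10% | 0.99 | 0.97 | 0.95 | 0.80 |
| 15% | 0.80 | 0.75 | 0.68 | 0.47 |
| 20% | 0.56 | 0.51 | 0.45 | 0.29 |

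**Step 3: the opposite direction.** With no true effect and a shift s away from zero, the noncentrality is √10 × s/SD. The chance of a false significant difference, 0.05 without a shift, becomes:

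| SD of paired difference | s = 1% | s = 2% | s = 5% |
|---|---|---|---|
| 10% | 0.06 | 0.09 | 0.29 |
| 15% | 0.05 | 0.07 | 0.16 |
| 20% | 0.05 | 0.06 | 0.11 |

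**The case against.** The strongest reply is that this is silence, not a flaw. The masked party is not named, so single blind could describe a masked image reader, and coded reading may already be the practice. This stands to the extent that a reader might infer from the plan that the flow reader is unmasked, and the documents do not say so. It does not dispose of the point. The ordinary meaning leaves the reader exposed, and nothing in the plan commits anyone to coded reading.

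A second reply concerns size. It is tempting to argue that flow scales with vessel area, so that a 2–3% slip in radius gives a 4–6% error in flow and power drops to 0.47. That holds only for a flat velocity profile. With a parabolic profile the error is 0.2–0.3%, because the slowest blood is at the wall; an outline drawn too wide mostly adds near-static tissue. If segmentation is automated, the mechanism largely disappears. The shift must also run the same way, differently on the two glucose days, across repeated scans ("On each study day, 11 MRI scans are performed") and across patients. All of this stands: the 5% shift is an upper-end assumption, and the power figures are conditional illustrations.

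A third reply is that coding does not restore full blinding. This is also correct. Staff who know the infusion can still influence slice placement or repeat scans, and a reader who also acquired the images may recognise them despite new labels. A reader might infer that coding would remove all bias from single blinding; it addresses only the calculation step.

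**Conclusion.** The point holds as a gap in protection of the primary outcome. The plan does not say who is masked and describes no masking where SMA flow is calculated; on the usual reading of single blind, the primary contrast is open to the influence of a reader who expects no effect. It is not a demonstrated bias.

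Its size and direction cannot be derived from the documents. On the assumptions in the working, with an SD of 15%, the cost in power runs from about 0.06 (0.80 to 0.75, unrounded 0.803 to 0.748) for a 1% shift to about 0.33 (0.80 to 0.47) for a 5% shift, and it is nil if the reading is already masked. The case for acting rests on how little the safeguard costs and on its covering the primary outcome, not on any one of these figures.

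**What to change.** 1. Before flow is calculated, replace patient, visit-date and infusion labels on every PC-MRI file with a random code. Whoever already calculates flow then processes the files in coded order.
2. Release the code only after the flow dataset is locked.
3. Beside the words single blind in the Design section, state who is masked, and whether the person calculating flow also acquires the scans. If so, acknowledge that masking may be incomplete.
4. If flows have already been calculated unmasked, do a coded re-read of the SMA scans from interventions 2 and 4, which covers the primary contrast. If reading was already masked, item 3 is all that is needed.

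**Cost.** A sentence or two in the plan and a relabelling step, with no extra patient or scan. With one study day per intervention, full coding covers at most 10 × 4 × 11 = 440 scans, and the re-read at most 10 × 2 × 11 = 220. The re-read is the only substantial work, and it arises only if flows were calculated unmasked.

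### Does the one-sentence mixed-model description give the antagonist-versus-saline comparison too small a standard error?

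*Combined protocol and SAP*

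**What the plan says.** Under Statistical analysis and graphs, the combined protocol and SAP gives the model in one sentence: flow is analysed by "a linear mixed model, that pairs the data, and compared the interventions after steady state of the infusion of GIPR antagonist". The next sentence fixes the comparison: "The primary statistical analysis will be done between the two interventions", which it lists as antagonist with oral glucose and saline with oral glucose. On reporting, it says that a "data table will present the flow measurements of each intervention, including mean and 95% confidence intervals".

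Methods and outcomes names the main outcome as "blood flow in superior mesenteric artery" and gives the schedule: "On each study day, 11 MRI scans are performed (-35 min to 80 min after oral fluid intake". Flow is measured "during the infusion of either saline or GIP receptor antagonist", so each series of scans belongs to one infusion. The Design entry reads "Randomized, placebo controlled, crossover, single blind design in 10 patients with type 2 diabetes". The Hypothesis entry expects that "antagonization of GIP receptor postprandially will have minor to none effect on the redistribution of blood flow" in these patients.

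The document does not state:

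- the rows of the analysis (scans, or one value per visit);
- the minute at which the steady-state window opens;
- whether flow is averaged over that window or read at one time;
- any random effect beyond what pairing implies;
- the method for degrees of freedom.

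It also gives no variance, no correlation between scans and no sample-size calculation.

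**The concern.** Treatment is given to a visit, not to a scan. Scans taken on one day share that day's physiology and set-up, so they may resemble each other more than scans of the same patient on another day. A model with a patient intercept alone does pair the data, but with scans as rows it treats same-day scans as independent replicates of the treatment. The standard error of the averaged difference between visits is then too small, and the residual degrees of freedom are too many.

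This would matter because little or no effect of the antagonist is expected. A standard error that is too small could turn an ordinary day-to-day difference into an apparent GIP effect, or make an interval around no effect look more precise than it is. The only intervals the plan mentions are per intervention, so the reader cannot tell from the plan how the uncertainty of the difference will be obtained.

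**Working it through.** The document has no figure to reproduce, so the check asks how much the unstated choice could matter.

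**Inputs from the document.** n = 10 patients, four interventions, primary contrast between the two glucose visits, 11 scans from -35 to 80 min.

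**Assumed inputs.**
- Two-sided 5% test.
- m = 4, 6 or 8 scans in the window. Even spacing would be 115/10 = 11.5 min, which puts 7 of the 11 scans after intake.
- Same-day correlation beyond the patient effect, ρ = 0 to 0.5, with within-patient variance set to 1.

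**Formulas for the time-averaged contrast**, with J visits in the model, scans as rows, scan time fitted and a patient intercept only:

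- True variance = 2[ρ + (1−ρ)/m]/n
- Expected reported variance = 2[(1−ρ) + m(n−1)(J−1)ρ/df]/(nm), with df = nJm − n − J − m + 2

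**Worked case: J = 2, m = 6, ρ = 0.3.**
- df = 120 − 10 − 2 − 6 + 2 = 104.
- True variance = 2(0.3 + 0.7/6)/10 = 0.0833, so SE 0.289.
- Reported variance = 2(0.7 + 16.2/104)/60 = 0.0285, so SE 0.169.
- Ratio of reported to true SE = 0.169/0.289 = 0.585.

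At ρ = 0 both variances reduce to 2/(nm), and the ratio is 1.

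**Type I error with the patient intercept only** (20,000 simulated trials per setting, two visits; SE ratio in brackets):

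| Scans | df | ρ = 0 | ρ = 0.1 | ρ = 0.3 | ρ = 0.5 |
|---|---|---|---|---|---|
| 4 | 66 | 4.9% (1.00) | 9.0% (0.86) | 18.5% (0.67) | 27.7% (0.56) |
| 6 | 104 | 5.0% (1.00) | 11.4% (0.80) | 24.5% (0.59) | 36.1% (0.47) |
| 8 | 142 | 5.0% (1.00) | 14.5% (0.75) | 30.7% (0.52) | 42.1% (0.41) |

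With all four visits in the model, the range for ρ = 0.1 to 0.5 is 9.1 to 38.5%.

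**Other readings that fit the same sentence:**

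- One value per visit, compared as paired differences on 10 − 1 = 9 df: 4.7 to 5.3% in every setting.
- Scans as rows with intercepts for patient and for visit within patient, Satterthwaite df: 3.7 to 5.2%, from about 1,000 fits in each of four settings (4 or 8 scans, ρ = 0.1 or 0.5).
- Contrast at one scan time in an intervention-by-time model, patient intercept only: 5.3 to 5.7% at ρ = 0.1 and 8.5 to 9.0% at ρ = 0.5. For m = 6 and ρ = 0.5, the mean reported SE is 0.392 against a true √(2/10) = 0.447.
- Scan time left out: the answer depends on the assumed flow curve and where the scans fall on it. With 4 scans, ρ = 0.1 and a half-sine rise of 2 within-patient SD, the error is 2.0% if the end scans sit at the zeros of the curve and 7.2% if all scans lie inside it. Nothing general can be drawn from this case.

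A large excess therefore needs four things together: scans as rows, no visit-level term, a time-averaged contrast, and positive same-day correlation. The document states none of them.

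**The case for a change.** The strongest case for a change is that a pre-specified plan should not leave readings with error rates of 5% and 42% both compliant. Eleven scans per visit and a mixed model invite scan-level rows, and a patient intercept is the simplest term that pairs the data. No fuller plan is cited, and the gap is not a redaction, since the sentence is complete. One added model term or one averaging step would close it.

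Two parts of this stand. The detail is missing, and the arithmetic for the patient-intercept model is right.

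The step from missing detail to a faulty standard error does not stand. In a two-treatment comparison within patients, one value per intervention per patient is at least as natural a meaning of pairing, and it is valid. No point in the assumed correlation range, zero included, is favoured by anything in the document.

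The window is also less open than it seems. The comparison is limited to steady state and to the two glucose visits, and the Aim and Hypothesis both concern flow after intake. What is missing is the exact minutes. The interval for the difference is a reporting matter: the planned table describes each intervention, and any mixed-model comparison yields an estimate and a standard error for the contrast.

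**Conclusion.** The concern does not call for a change. The plan names the outcome, the two visits compared, the paired structure and the period in words. It leaves rows, scan minutes, summary and error term to the analyst. The usual ways of completing a paired crossover analysis, one value per visit or a visit-level random term, keep the type I error near 5%.

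The 9 to 42% figure belongs to one particular completion that the plan does not adopt. It rests on an assumed 4 to 8 scans per visit, same-day correlation of 0.1 to 0.5, two visits in the model and a time-averaged contrast. It falls to 5% at zero correlation and to about 5 to 9% for a single-time contrast. If that completion were used with residual degrees of freedom, a report giving them would reveal it: 66 to 142, where the paired analysis has 9.
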